#### 10.4. Booster Period

During the Booster Period, eligible subjects will receive booster vaccinations, consisting of 4 weekly injections ([Table 14](#)). If the subject has fever  $\geq 38.0^{\circ}\text{C}$  and/or elevated IL-6  $\geq 500$  pg/mL, proceed with the visit but omit study treatment administration; if fever abates and

cytokines diminish to <500 pg/mL, the subject may proceed with the next scheduled dose after approval from the medical monitor). In addition, if a subject exhibits  $\text{IFN}\gamma \geq 1000$  pg/mL, the Elicio medical monitor should be contacted for consultation.

At **Visit 12 (Day 196)**, the following visit procedures will include:

- Administer the EORTC QLQ-C30 and the tumor type-specific PRO (see [Section 11.3](#)).
- Perform a physical examination, which will be based on institution standard of care (see [Section 12.1.3](#)).
- Record vital signs (blood pressure, pulse rate, body temperature, and respiratory rate). Measurements will be obtained after 3 minutes in the sitting position. No other measurements or procedures were performed during this 3-minute period.
- Record weight.
- Confirm ECOG Scale of Performance Status.
- Record any change in concomitant medications since the previous visit.
- All laboratory samples should be taken prior to dosing on any study visit that has dosing.
  - Collect a blood sample for clinical laboratory assessments, including the cytokine panel (local laboratory; see [Section 11.1](#) and [Section 12.1.6](#)). Note: cytokine testing should be performed and reviewed within 7 days prior to dosing.
  - Collect a blood sample for ctDNA (to be performed at a central laboratory).
- Record any AEs since last visit. Check for signs of toxicity, including fever and laboratory evidence of elevated cytokines. Hold the ELI-002 dose if Grade  $\geq 2$  CRS is present, or if elevated cytokine IL-6 is present. If elevated  $\text{IFN}\gamma$  is present, the Elicio medical monitor should be contacted for consultation ([Section 6.8.1](#)).
- **Dose 7:** Trial drug administration and subjects must be observed for safety for at least 1-hour postdose.
- Subjects will be provided with the reactogenicity diary to complete for 7-days following the dose. Subjects will be instructed how to complete the diary and to return the completed form at their next visit.

At **Visit 13 (Day 203)**, the following visit procedures will include:

- Administer the EORTC QLQ-C30 and the tumor type-specific PRO (see [Section 11.3](#)).
- Perform a physical examination, which will be based on institution standard of care (see [Section 12.1.3](#)).
- Record vital signs (blood pressure, pulse rate, body temperature, and respiratory rate). Measurements will be obtained after 3 minutes in the sitting position. No other measurements or procedures were performed during this 3-minute period.

- Record weight.
- Confirm ECOG Scale of Performance Status.
- Record any change in concomitant medications since the previous visit.
- All laboratory samples should be taken prior to dosing on any study visit that has dosing.
  - Collect a blood sample for clinical laboratory assessments, including the cytokine panel (local laboratory; see Section 11.1 and Section 12.1.6). Note: cytokine testing should be performed and reviewed within 7 days prior to dosing.
- Record any AEs since last visit. Check for signs of toxicity, including fever and laboratory evidence of elevated cytokines. Hold the ELI-002 dose if Grade  $\geq 2$  CRS is present, or if elevated cytokine IL-6 is present. If elevated IFN $\gamma$  is present, the Elicio medical monitor should be contacted for consultation (Section 6.8.1).
- **Dose 8:** Trial drug administration and subjects must be observed for safety for at least 1-hour postdose.
- Subjects will be provided with the reactogenicity diary to complete for 7-days following the dose. Subjects will be instructed how to complete the diary and to return the completed form at their next visit.

At Visit 14 (Day 210), the following visit procedures will include:

- Administer the EORTC QLQ-C30 and the tumor type-specific PRO (see Section 11.3).
- Perform a physical examination, which will be based on institution standard of care (see Section 12.1.3).
- Record vital signs (blood pressure, pulse rate, body temperature, and respiratory rate). Measurements will be obtained after 3 minutes in the sitting position. No other measurements or procedures were performed during this 3-minute period.
- Record weight.
- Confirm ECOG Scale of Performance Status.
- Record any change in concomitant medications since the previous visit.
- All laboratory samples should be taken prior to dosing on any study visit that has dosing.
  - Collect a blood sample for clinical laboratory assessments, including the cytokine panel (local laboratory; see Section 11.1 and Section 12.1.6). Note: cytokine testing should be performed and reviewed within 7 days prior to dosing.
  - Collect a whole blood sample for immunogenicity testing (central laboratory).
- Record any AEs since last visit. Check for signs of toxicity, including fever and laboratory evidence of elevated cytokines. Hold the ELI-002 dose if Grade  $\geq 2$  CRS is

- present, or if elevated cytokine IL-6 is present. If elevated IFN $\gamma$  is present, the Elicio medical monitor should be contacted for consultation ([Section 6.8.1](#)).
- **Dose 9:** Trial drug administration and subjects must be observed for safety for at least 1-hour postdose.
  - Subjects will be provided with the reactogenicity diary to complete for 7-days following the dose. Subjects will be instructed how to complete the diary and to return the completed form at their next visit.

At **Visit 15/ End of Treatment (Day 217)**, this visit is to be performed when the subject completes the treatment period or if they discontinue treatment early and prior to entering the follow-up period of the study. The visit procedures will include:

- Administer the EORTC QLQ-C30 and the tumor type-specific PRO (see [Section 11.3](#)).
- Perform a physical examination, which will be based on institution standard of care (see [Section 12.1.3](#)).
- Record vital signs (blood pressure, pulse rate, body temperature, and respiratory rate). Measurements will be obtained after 3 minutes in the sitting position. No other measurements or procedures were performed during this 3-minute period.
- Record weight.
- Confirm ECOG Scale of Performance Status.
- Record any change in concomitant medications since the previous visit.
- All laboratory samples should be taken prior to dosing on any study visit that has dosing.
  - Collect a blood sample for clinical laboratory assessments, including the cytokine panel (local laboratory; see [Section 11.1](#) and [Section 12.1.6](#)). Note: cytokine testing should be performed and reviewed within 7 days prior to dosing.
- Record any AEs since last visit. Check for signs of toxicity, including fever and laboratory evidence of elevated cytokines. Hold the ELI-002 dose if Grade  $\geq 2$  CRS is present, or if elevated cytokine IL-6 is present. If elevated IFN $\gamma$  is present, the Elicio medical monitor should be contacted for consultation ([Section 6.8.1](#)).
- **Dose 10:** Trial drug administration and subjects must be observed for safety for at least 1-hour postdose.
- Subjects will be provided with the reactogenicity diary to complete for 7-days following the dose. Subjects will be instructed how to complete the diary and to return the completed form at their next visit.

## 10.5. Follow-up Period

A Follow-up Period will provide safety and efficacy data ([Table 15](#) and [Table 16](#)).

At every visit during the Follow-up Period, **Visit 16 (Day 231), Visit 17 (Day 259), Visit 18 (Day 315), Visit 19 (Day 399), Visit 20 (Day 483), Visit 21 (Day 567), Visit 22 (Day 651), Visit 23 (Day 735), Visit 24 (Day 819), Visit 25 (Day 903), Visit 26 (Day 987), Visit 27 (Day 1071) and Visit 28/End of Study (Day 1127)**, the following visit procedures will include:

- Confirm ECOG Scale of Performance Status.
- Collect a blood sample for ctDNA test (central laboratory).
- Record any AEs that occur within 30 days of last dose and follow any such AEs until they resolve or return to baseline level.

In addition, the following assessments will be conducted at these Follow-up visits:

At **Visit 16 (Day 231)**, the following visit procedures will include

- Collect a blood sample for clinical laboratory assessments, including the cytokine panel (local laboratory; see [Section 11.1](#) and [Section 12.1.6](#)).
- Collect a whole blood sample for immunogenicity testing (central laboratory).

At **Visit 16 (Day 231), Visit 17 (Day 259), Visit 18 (Day 315), Visit 19 (Day 399), Visit 20 (Day 483), Visit 21 (Day 567), Visit 22 (Day 651), Visit 23 (Day 735), and Visit 24 (Day 819)** the following visit procedures will include

- Administer the EORTC QLQ-C30 and the tumor type-specific PRO (see [Section 11.3](#)).
- Record vital signs (blood pressure, pulse rate, body temperature, and respiratory rate). Measurements will be obtained after 3 minutes in the sitting position. No other measurements or procedures were performed during this 3-minute period.
- Record weight.

At **Visit 17 (Day 259), Visit 19 (Day 399), Visit 20 (Day 483), Visit 21 (Day 567), Visit 22 (Day 651), Visit 23 (Day 735), Visit 24 (Day 819), Visit 25 (Day 903), Visit 26 (Day 987), Visit 27 (Day 1071), and Visit 28/End of Study (Day 1127)**, the following visit procedures will include:

- Perform a CT ( $\pm 14$  days) with contrast. For subjects with IV contrast allergy/intolerance, MRI may be performed. The same modality as the screening imaging assessment should be used throughout the trial.
- Collect a serum sample for CA-125/CA 19-9/CEA for appropriate tumor type (local laboratory).

At **Visit 20 (Day 483)**, the following visit procedures will include:

- Perform a physical examination, which will be based on institution standard of care (see [Section 12.1.3](#)).

At **Visit 22 (Day 651)**, the following visit procedures will include:

- Collect a whole blood sample for immunogenicity testing (central laboratory).

The **Visit 28/End of Study** visit will be scheduled for subjects who complete the study or for any subject that discontinues from the study early.

## 11. CLINICAL ACTIVITY, IMMUNE ASSESSMENTS, AND SUBJECT REPORTED OUTCOMES

Clinical activity, immune assessments, and PROs will be collected according to the Schedule of Assessments (Table 11, Table 12, Table 13, Table 14, Table 15, and Table 16).

Median RFS and 1-year RFS rate will be assessed through CT imaging with contrast as assessed by the site investigators using iRECIST criteria [Seymour et al, 2017]; subjects will be followed for OS. Unscheduled CT or MRI imaging may be performed at any time, if the investigator determines that there are clinical signs of disease progression.

In addition, biomarker response rate will be based on the percentage of subjects achieving biomarker reduction or clearance, as measured by the absence or decrease of ctDNA from baseline and the duration of ctDNA clearance and/or reduction, or if ctDNA was not detectable at baseline, serum tumor biomarker (such as carbohydrate antigen [CA]19-9, carcinoembryonic antigen [CEA], and CA-125) reduction and clearance compared to baseline will be recorded. T cell responses in PBMCs will be assessed by immune assays such as IFN $\gamma$  Fluorospot, ICS, and/or dextramers.

Immune responses will be correlated to clinical efficacy parameters.

### 11.1. Immunogenicity

Patients will have leukapheresis and blood samples drawn to evaluate the immunogenicity of ELI-002. T cell responses in PBMCs will be assessed by immune assays such as IFN $\gamma$  Fluorospot, ICS, and/or dextramers. Serum cytokine, CA-125, CEA and CA 19-9 levels will also be examined.

**HLA Typing:** High resolution HLA typing will be used to identify certain individual variations in the immune system. Cohorts will be enrolled regardless of the HLA subtype.

**Serum Cytokines:** Concentrations of cytokines, IL-2, IFN $\gamma$ , IL-6, IL-10, and TNF $\alpha$ , will be measured using multiplex technology in serum samples (local laboratory).

**Cellular immune response:** The cellular immune response to ELI-002 will be monitored by examining T cell responses using immune assays such as Fluorospot and ICS. The Fluorospot assay enumerates the release of IFN $\gamma$  in human PBMCs following KRAS peptide stimulation. The ICS assay is a flow cytometry-based assay that can detect cytokine production by CD4+ and CD8+ T cells to the KRAS peptides. For both assays, PBMCs will be stimulated individually with mKRAS peptide pools to determine the frequency of KRAS-specific T cells per patient and timepoint. Dextramers are fluorescently labeled HLA multimers that can detect antigen-specific T cells. In subjects with HLA alleles for which dextramer(s) are available, the frequency of KRAS-specific T cells can be monitored in PBMCs before and after vaccination.

Full details of the leukapheresis or phlebotomy procedure to obtain PBMCs will be provided in the Central Laboratory Manual.

**Standard of Care Biopsies:** Tumor tissue specimens will be collected post-dosing from biopsies performed as standard of care per iRECIST criteria (ie; following observation of new lesions on radiographic imaging and investigator assessment that tissue can be safely obtained). If there is sufficient sample collected, the pathology laboratory should perform in situ gene

expression and/or IHC staining to examine tumor-infiltrating T cells and the tumor microenvironment.

## 11.2. Tumor Tissue Collection at Surgery

Once a subject has consented, and depending on the clinical site location, the trial coordinator will requisition a tumor tissue sample that was collected at surgery. Details for tumor tissue collection are provided in the Central Laboratory Manual).

## 11.3. Patient Reported Outcomes

Patient reported outcomes will be assessed by EORTC QLQ-C30 and QLQ-PAN26, QLQ-CR29, QLQ-OV28, QLQ-BIL21 or QLQ-LC13 and will be administered to subjects according to the Schedule of Assessments and prior to other visit procedures (Table 11, Table 12, Table 13, Table 14, Table 15, and Table 16). All the PROs have been fully validated by EORTC, except QLQ-PAN26, which has completed phase III of validation and is on-track for full validation in 2021. Verification of validation can be obtained through EORTC, and the list of questionnaires and the phase of validation can be found at the following site:

<https://qol.eortc.org/questionnaires/>.

### 11.3.1. EORTC QLQ-C30

The European Organization for Research and Treatment of Cancer quality of life questionnaire (EORTC QLQ-C30) is a tool for assessing the quality of life (QoL) of cancer subjects participating in clinical trials. The EORTC QLQ-C30 incorporates 9 multi-item scales: 5 functional scales (Physical, Role, Cognitive, Emotional and Social Functioning); 3 symptom scales (Fatigue, Pain and Nausea/Vomiting); and a Global Health Status/QoL scale. Six single item scales are also included (Dyspnoea, Insomnia, Appetite Loss, Constipation, Diarrhoea and Financial Difficulties). The psychometric properties of the questionnaire have been determined to be valid, reliable, and sensitive [Aaronson et al, 1993; Osoba et al, 1994; Kaasa et al, 1995].

### 11.3.2. Tumor type-specific PROs

Tumor type-specific PROs are intended to supplement the EORTC QLQ-C30 with questions appropriate for the symptoms experienced by subjects with each tumor type. Please refer to the EORTC website for the PRO validation documentation. Tumor type-specific PROs will include:

- QLQ-PAN26: pancreatic cancer
- QLQ-BIL-21: biliary cancer
- QLQ-CR-29: colorectal cancer
- QLQ-LC-13: lung cancer
- QLQ-OV-28: ovarian cancer

#### **11.4. ctDNA Levels**

Levels of ctDNA (mean tumor molecules/mL) will be assessed using a ctDNA assay (central laboratory) in anticoagulated peripheral whole blood at indicated timepoints post vaccination. The ctDNA fold change from baseline will be calculated at each timepoint.

If a subject is MRD by ctDNA at screening, sites may continue to monitor ctDNA levels per their standard of care testing and rescreen if the subject becomes MRD+ by ctDNA analysis. It is recommended that the time between ctDNA screening tests be  $\geq 90$  days.

## **12. ASSESSMENT OF SAFETY**

### **12.1. Safety Parameters**

#### **12.1.1. Demographics and Medical History**

Demographic variables will include age, gender, and race/ethnicity. Medical and medication history, including cancer history/prior treatments, current medications (prescription, herbal and dietary supplements, over-the-counter medications, and topical treatments), smoking history (for NSCLC subjects only), and diseases will be assessed at Screening and recorded in the source documents and the eCRF.

Weight and height will be collected during the Screening Period and weight will be collected throughout the trial according to the Schedule of Assessments ([Table 11](#), [Table 12](#), [Table 13](#), [Table 14](#), [Table 15](#), and [Table 16](#)).

#### **12.1.2. Vital Signs**

Vital signs will be collected throughout the trial according to the Schedule of Assessments ([Table 11](#), [Table 12](#), [Table 13](#), [Table 14](#), [Table 15](#), and [Table 16](#)) and will include blood pressure, pulse rate, body temperature, and respiratory rate. Measurements will be obtained after 3 minutes in the sitting position. No other measurements or procedures were performed during this 3-minute period.

#### **12.1.3. Physical Examinations**

Full or targeted PEs will be performed at screening and at specified times during the trial ([Table 11](#), [Table 12](#), [Table 13](#), [Table 14](#), [Table 15](#), and [Table 16](#)) based on standard of care.

#### **12.1.4. Electrocardiogram**

A resting 12-lead ECG will be performed according to the Schedule of Assessments ([Table 11](#) and [Table 12](#)) and reviewed by a cardiologist or clinical investigator, per institutional guidelines and practice.

#### **12.1.5. Eastern Cooperative Oncology Group**

The ECOG Scale of Performance Status describes a subject's level of functioning in terms of their ability to care for themselves, daily activity, and physical ability (walking, working, etc.).

Eligibility for this trial requires a subject's ECOG performance status to be 0 to 1 (see [Table 24](#)).

The ECOG assessment will be performed according to the Schedule of Assessments ([Table 11](#), [Table 12](#), [Table 13](#), [Table 14](#), [Table 15](#), and [Table 16](#)).

#### **12.1.6. Laboratory Assessments**

Laboratory tests will be performed according to the Schedule of Assessments ([Table 11](#), [Table 12](#), [Table 13](#), [Table 14](#), and [Table 15](#)). A central clinical laboratory will be utilized for biomarkers, but local clinical laboratories will be used for safety assessments.

The results of clinical laboratory tests conducted during the trial will be assessed by the investigator to determine each subject's appropriateness for trial participation.

For the remainder of the trial, the investigator will review laboratory values that are outside the normal reference ranges to determine whether the values are clinically significant. Clinically significant changes will be followed until the parameter returns to Baseline or until the investigator determines that follow-up is no longer medically necessary. Clinically significant values will be documented as Adverse Events as described in Section 12.2.1.1. Unscheduled re-tests may be performed as needed through the Follow-up Visit.

#### **12.1.6.1. Hematology**

The following hematology parameters will be assessed:

- White blood cell count
- Absolute/% Neutrophils
- Absolute/% Lymphocytes
- Absolute/% Monocytes
- Absolute/% Eosinophils
- Red blood cell count
- Hematocrit
- Hemoglobin
- Platelet Count
- Absolute/% Basophils

#### **12.1.6.2. Coagulation**

The following coagulation parameters will be assessed:

- Prothrombin time (PT)
- Partial Thromboplastin time (PTT)
- International Normalized Ratio (INR)
- Fibrinogen
- D-dimer

#### **12.1.6.3. Blood Chemistry**

The following blood chemistry parameters will be assessed:

- Sodium
- Potassium
- Chloride
- Creatinine
- Calcium
- Phosphate
- Glucose
- Alkaline phosphatase
- Lactate dehydrogenase
- Blood urea nitrogen (BUN)
- BUN/creatinine ratio
- Bilirubin (total)
- Protein (total)
- Albumin
- Uric acid
- Aspartate transaminase (AST)

- Bicarbonate
- LDH
- Magnesium
- Alanine transaminase (ALT)
- Creatine kinase
- Ferritin
- C-reactive protein (CRP)

#### **12.1.6.4. Serum Cytokines**

The following serum cytokines will be assessed:

- IL-2
- IFN $\gamma$
- IL-6
- IL-10
- TNF $\alpha$

#### **12.1.6.5. Viral Laboratory Testing at Screening**

The following viral parameters will be assessed at Screening only:

- Hepatitis C RNA
- COVID-19 active infection

#### **12.1.6.6. Pregnancy Screen**

A urine pregnancy test will be performed according to the Schedule of Assessments ([Table 11](#)) for women of childbearing potential. Postmenopausal women must have been amenorrhoeic for at least 12 months to be considered of non-childbearing potential. Childbearing status for all women will be recorded in the source documents and in the eCRF.

A positive pregnancy test will exclude the subject from participation in the trial. Any clinically abnormal or inconclusive test will be repeated.

## **12.2. Adverse and Serious Adverse Events**

### **12.2.1. Definition of Adverse Events**

#### **12.2.1.1. Adverse Event**

An AE is the development of an undesirable medical condition or the deterioration of a pre-existing medical condition following or during exposure to a pharmaceutical product, whether or not considered study-drug related. An AE can be any unfavorable and unintended sign, symptom of disease temporally associated with the use of study drug, without any judgement about causality (see current ICH guidelines).

In this study, investigators should report AEs based on CTCAE v5.0 criteria, or ASTCT consensus criteria in the event of either CRS or immune effector cell associated neurotoxicity

syndrome (ICANS). Treatment-emergent AEs (TEAEs) are defined as events not present prior to the initiation of study drug or any event already present that worsens in either intensity or frequency following exposure to study treatment. AEs must be recorded in the eCRF and on forms as provided by Elicio.

An AE does not include the following:

- Medical or surgical procedures (eg, surgery, endoscopy, dental extraction, transfusion); the condition that necessitates the procedure is the AE
- Any pre-existing disease or condition, or laboratory or ECG abnormality, which is present prior to the start of the study medication and that does not worsen
- Laboratory or ECG abnormalities without clinical significance (ie, those which do not require medical intervention or that do not result in discontinuation or interruption of the study drug)
- Situations where an adverse medical event has not occurred (ie, hospitalization for elective surgery, social admission)
- Overdose of study medication or any concomitant medication without any signs or symptoms, unless the subject is hospitalized for observation

The time period for collecting and documenting AEs for each subject begins from the time the subject is administered the first dose of study drug through end of treatment (EOT) or early discontinuation of treatment.

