**Primary Endpoints:**

- To define the MTD of ELI-002 (in the event there is an MTD) and the RP2D
- To evaluate safety as assessed by the incidence of adverse events (AEs) and clinically significant changes in laboratory tests and vital signs

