### 6.7.3. Dose-limiting Toxicity Guidelines

A DLT will be defined as any event at least possibly related to ELI-002 as follows:

- a. Any Grade  $\geq 3$  non-hematologic toxicity except asymptomatic laboratory abnormalities (see Section 12.2.1.1)
- b. Any Grade  $\geq 3$  toxicity involving major organ systems for greater than 72 hours and occurring within 28 days of subcutaneous administration
- c. Grade 3 CRS that does not resolve to  $\leq$  Grade 2 within 7 days
- d. Any Grade 4 CRS that does not improve to  $<$  Grade 2 within 72 hours
- e. Any Grade  $\geq 3$  autoimmune disorder
- f. Any Grade  $\geq 3$  rash that does not resolve to  $\leq$  Grade 1 within 7 days with appropriate treatment

The DLT observation period will be 28 days.

Maximum tolerated dose definition: The MTD is defined as the highest dose level with a DLT incidence  $<33\%$  of cohort subjects.

See protocol Section 6.7.1 and Section 6.8 for management of toxicity.

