## 10.2. Immunization Period

During the Immunization Period, subjects will receive 4 weekly SC injections (Weeks 1 to 4) followed by 2 injections at Week 6 and Week 8 (Table 12). If the subject has fever  $\geq 38.0^{\circ}\text{C}$  and/or elevated IL-6  $\geq 500$  pg/mL, proceed with the visit but omit study treatment administration; if fever abates and cytokines diminish to  $< 500$  pg/mL, the subject may proceed with the next scheduled dose after approval from the medical monitor). In addition, if a subject exhibits IFN $\gamma$   $\geq 1000$  pg/mL, the Elicio medical monitor should be contacted for consultation.

All laboratory samples should be taken prior to dosing on any study visit that has dosing.

At **Visit 3 (Baseline, Day 57) prior to trial drug administration**, the following visit procedures will include:

- Administer the EORTC QLQ-C30 and the tumor type-specific PRO (see Section 11.3).
- Record any change in medical history since the previous visit. Subjects must have recovered from surgery without any ongoing medical/surgical issues.
- Record any change in cancer history since the previous visit.
- Perform a physical examination which will be based on institution standard of care (see Section 12.1.3). In addition, a neurological examination for baseline assessment of ICANS/ICE will be performed.
- Record vital signs (blood pressure, pulse rate, body temperature, and respiratory rate).
- Record weight.
- Perform a 12-lead ECG (to be reviewed by a cardiologist or clinical investigator according to institutional guidelines and practice).
- Confirm ECOG Scale of Performance Status is 0 or 1.
- Record any change in concomitant medications since the previous visit.
- Collect a blood sample for clinical laboratory assessments, including the cytokine panel (local laboratory; see Section 11.1 and Section 12.1.6). Note: cytokine testing should be performed within 7 days prior to dosing.
- Collect a blood sample for ctDNA (to be performed at a central laboratory).
- Collect a blood sample for high resolution HLA typing (central laboratory).
- Record any pre-treatment SAEs that have occurred since the previous visit.

**Dose 1:** The first dose must be administered at the clinical site. Subjects must be observed by study staff for at least 1-hour postdose for observation and must stay within an hour of the clinic for  $\geq 24$  hours in order to monitor for potential AEs such as CRS.

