## 9.0 STUDY ENDPOINTS

### 9.1 Endpoints

#### 9.1.1 Phase 1 Primary Endpoints

- To define the MTD of ELI-002 (in the event there is an MTD) and the recommended Phase 2 dose (RP2D)
- To evaluate safety as assessed by the incidence of adverse events (AEs) and clinically significant changes in laboratory tests and vital signs

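### An *or* in the Protocol 12.2.1.1 exclusion, where *and* is needed, lets treated or dose-holding laboratory abnormalities fall outside the AE definition if sites read it literally

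*Protocol*

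**What the plan says.** Protocol 12.2.1.1 lists what is not an AE. One item is "Laboratory or ECG abnormalities without clinical significance", followed by a parenthesis introduced by *ie*: "those which do not require medical intervention or that do not result in discontinuation or interruption of the study drug".

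Protocol 12.1.6 says that after eligibility "the investigator will review laboratory values that are outside the normal reference ranges to determine whether the values are clinically significant", and then: "Clinically significant values will be documented as Adverse Events as described in Section 12.2.1.1". The judgement is the investigator's, but the reporting rule is the one in 12.2.1.1.

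The primary safety endpoint in the Protocol synopsis is the "incidence of adverse events (AEs) and clinically significant changes in laboratory tests and vital signs"; SAP 9.1.1 has the same wording. SAP 13.7.1 defines treatment-emergent AEs but gives no separate rule for laboratory findings.

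DLT criterion (a) in Protocol 6.7.3, repeated in the synopsis and in SAP 8.1, covers Grade 3 or higher "non-hematologic toxicity except asymptomatic laboratory abnormalities (see Section 12.2.1.1". Section 12.2.1.1 does not say what asymptomatic means.

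**The concern.** Because *ie* introduces a definition, the parenthesis is the operative test. The negative is stated afresh after *or*, so the sentence does not naturally read as neither one nor the other. To be an AE, an abnormality would have to require intervention and also stop or interrupt the drug. That is an unusually demanding test, and probably not the one meant.

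The schedule produces cases that fall between the two conditions:

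- **Dose withheld, no treatment.** Protocol 6.7.1 and 10.2 withhold a dose when the IL-6 criterion is met; at such a visit sites "proceed with the visit but omit study treatment administration". If nothing is given for the IL-6 value, the literal rule says it is not an AE. It would then also be missing from the listing of TEAEs leading to dose reduction or interruption planned in SAP 13.7.1.
- **Treated, dosing unaffected.** An electrolyte or liver-test abnormality that is treated, with the next dose given on time, is not an AE. No dose is scheduled between Day 106 and Day 196 (90 days), yet safety laboratories are drawn on Days 120, 148 and 176. An abnormality treated and resolved in that gap has no dose to interrupt.

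At stake is AE incidence in cohorts of 3 to 6 subjects, where one event more or less is visible. The wording can only lower the count. If some sites follow the head phrase and others the parenthesis, AE rates also become inconsistent across sites.

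**Working it through.** The plan states no figure on this point, so there is none to reproduce. The check is a truth table of the wording.

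Let A mean that the abnormality required medical intervention, and B that the drug was discontinued or interrupted.

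- As written: excluded if (not A) or (not B).
- With the conjunction changed: excluded if (not A) and (not B).

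| A: intervention | B: interruption | Excluded as written (*or*) | Excluded with *and* |
|---|---|---|---|
| no | no | yes | yes |
| no | yes | yes | no |
| yes | no | yes | no |
| yes | yes | no | no |

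The written rule excludes 3 of 4 combinations and the *and* rule 1 of 4. The two rows that change are those described above. These are unweighted logical cells, not a share of events.

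The documents give no rate for abnormalities in those two rows. For scale only, let p be an **assumed** per-subject probability of at least one such abnormality, independent between subjects. The expected number affected among n is n × p, and the chance of at least one is 1 − (1 − p)^n. I use n = 18 (planned total, Protocol 13.1) and n = 6 (largest planned cohort).

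| Assumed p | Expected of 18 | P(at least 1 of 18) | Expected of 6 | P(at least 1 of 6) |
|---|---|---|---|---|
| 2% | 0.36 | 0.31 | 0.12 | 0.11 |
| 5% | 0.9 | 0.60 | 0.3 | 0.27 |
| 10% | 1.8 | 0.85 | 0.6 | 0.47 |
| 20% | 3.6 | 0.98 | 1.2 | 0.74 |

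For example, with p = 5%: 18 × 0.05 = 0.9 and 1 − 0.95^18 = 0.60. SAP 8.1 lists two further cohorts, so the treated number may exceed 18.

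Where else the information would appear if the AE were not recorded:

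- Protocol 13.3.4: laboratory listing with change from baseline, shift tables for selected parameters, and dose interruptions listed.
- SAP 13.7.2: summaries of cytokines and of worst on-treatment hematology and chemistry, and listings with low/high flags. It specifies no shift tables, no coagulation summary, and no summary of clinically significant changes as such.
- SAP 13.5.1: summary of the reasons doses were not administered.

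The values survive. What can be lost is their status as AEs, which is the main route by which clinical significance reaches a summary table.

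**The case against.** The strongest reply is that no sensible investigator would apply the parenthesis literally. It glosses a phrase about clinical significance, and 12.1.6 both gives that judgement to the investigator and makes reporting a duty. Other text points the same way. The general Grade 1 description in 12.4 includes findings needing no intervention. The supplementary scale in 12.5 has a moderate category for events that may be treated, and ties interruption of study medication only to the severe category. These sit badly with a rule that an AE must be both treated and dose-interrupting. This stands to the extent that the undercount is possible, not established. It does not remove the defect, because 12.1.6 refers back to 12.2.1.1 and nothing restates the rule correctly.

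It also stands that the safety committee reviews clinical laboratory data alongside AEs when deciding on escalation, and that a clinical condition behind a laboratory value remains an AE in its own right.

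Three stronger readings are tempting but not supported:

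- **That every laboratory and ECG abnormality after the last dose is lost, since nothing remains to interrupt.** After the Day 217 sample, the following 30 days contain one scheduled safety-laboratory draw (Visit 16, Day 231). The AE window itself is unsettled: 12.2.1.1 ends collection at end of treatment, while 12.7 runs to 30 days afterwards.
- **That ECG findings are materially affected.** Scheduled ECGs are at Visit 2 and before dosing at Visit 3; SAP 13.7.5 calls later ones discretionary.
- **That the DLT count is diluted.** Criterion (a) turns on whether the abnormality is asymptomatic, not on intervention or interruption, and criterion (b) has no laboratory exception. The documents show an unclear cross-reference, not a widened exemption.

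**Conclusion.** The definition is wrong as written. Taken literally, it excludes treated abnormalities that did not affect dosing and untreated abnormalities that did, and section 12.1.6 does not repair it. AE incidence could therefore be undercounted or inconsistently reported; any error lowers the count. This rests on sites applying the parenthesis as written. The size cannot be derived: 3 of 4 against 1 of 4 describes the logic, and the probabilities above rest on assumed rates. The laboratory data are not lost, so the effect is confined to AE classification and the tables built on it. This is a drafting correction worth making, not evidence that toxicity has been missed.

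**What to change.** In Protocol 12.2.1.1, replace the *or* joining the two negative clauses with *and*, so that an abnormality is excluded only if it neither needed intervention nor led to discontinuation or interruption. Carry the same wording into the CRF completion guidance.

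An amendment will not recode events already collected. The synopsis planned last enrolment for 2Q2023, the SAP is headed as the final analysis, and SAP 14.0 records early termination of long-term follow-up. If collection is complete, compare the laboratory listings with concomitant medications and the recorded reasons for doses not given, query the sites on mismatches, add confirmed missed events to the AE tables, and describe the step in the CSR. All three sources are already planned outputs.

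Two related places need reconciling. The laboratory exception in 6.7.3(a) and its cross-reference to 12.2.1.1 must be made consistent, since that section does not define the term used; no DLT rule is proposed here. The AE collection windows in 12.2.1.1 and 12.7 must also agree.

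The cost is one word in the protocol, a slightly higher AE count and a little extra data review.
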